## Survey of QRS frequency at various left ventricular pacing sites for cardiac resynchronization.

### Background

Many heart failure patients with prolonged QRS complexes are candidates for cardiac resynchronization therapy (CRT). The accepted rationale for CRT is that the widened QRS slows left ventricular (LV) activation to such a degree that the contraction is dyssynchronous and the ejection of blood is significantly reduced. CRT is performed by the addition of a separate pacing lead within a branch of the coronary sinus (or surgically implanted on the LV surface) and pacing at that site simultaneously with right ventricular pacing. Clinical studies have shown that patients with certain widened QRS patterns, such as left bundle branch block (LBBB), are more likely to exhibit contractile as well as clinical improvement. However, not all patients exhibit improvement. Improving the patient selection criteria for CRT based on intrinsic QRS properties as well as LV site of pacing has been an active area of clinical study.

We have shown that frequency spectrum analysis of the intrinsic QRS complex using the Fourier transform algorithm can help identify patients who are likely to improve (AKA: responders). In addition, we have shown that the reduction of QRS low frequency power in certain ECG leads (in particular lead V3) shortly following implant also predicts CRT responders. We hope to begin a prospective trial to select the optimal LV pacing site based on paced QRS frequency characteristics. However, the effect of various locations of LV pacing sites on the resultant QRS frequency characteristics is not precisely known within any given patient. This study will provide us with more complete, spatially distributed QRS data in order to determine the variability in frequency signals between known locations. In this way, we will be able to design the eventual prospective study by utilizing the variance of frequency results we determine in this study to determine the study size required and specific frequency goals.

### Research procedures:

Patients who are scheduled to undergo implantation of a left ventricular pacing lead via the coronary sinus branch veins will be approached for enrollment. This will include new CRT device implants (pacemaker or ICD) or upgrade of a currently implanted pacemaker or ICD. Patients will be approached during clinical outpatient clinic visits as well as preprocedural visits just prior to entering the laboratory for the scheduled implant. We will plan to enroll an equal (or near equal) number of male and females for a total of 20-30 subjects (depending on the encountered variability of results).

After cannulation of the coronary sinus, a clinically approved Biotronik Vision guidewire will be advanced into 3 coronary sinus branch veins receiving venous blood from the anterior, lateral and posterior regions of the left ventricle. This 0.014 in guidewire is electrically insulated except for a 15 mm section near the distal tip. When connected via the 30mm uninsulated section near the proximal end to a pacing circuit, it allows pacing impulses to be delivered to selected sites within the venous branch. In each branch vein, 3 pacing sites will be tested: apical, mid ventricular and basal. We will test the anterior and posterior veins first, and then test the usually targeted lateral vein. Then, after all 3 sites within the

lateral vein are tested, a standard LV pacing lead will be advanced over the guidewire, in the usual clinical manner, for final placement of that lead. The additional time required to position and pace the 3 sites (alone and in combination with a previously implanted RV pacing lead) should not exceed 5-10 minutes, with <2 minutes of fluoroscopy. In this manner, nine distributed sites around the LV will be assessed. The procedural and fluoroscopic time required to locate and test each site will be measured starting after placing the coronary sinus delivery sheath until the delivery of the LV lead over the guidewire.

The sensed and paced QRS complexes in the normal ECG limb leads and lead V3 will be saved digitally on our laboratory monitoring system (GE Prucka). These ECG signals will be then analyzed by our frequency algorithm, in which we will manually isolate the QRS complex for time frequency analysis in which the complex will be divided into 48 time segments. The algorithm will determine the average frequency of each segment and we will then average the first 16 segments together to represent the initial third of the QRS, the middle third will be derived from the next 16 segments and the final third from the remaining segments. We will then compare the frequency data from these QRS segments between the nine different ventricular locations to derive the positional variability. Once this is obtained, we should be able to determine the sample sizes required for a randomized comparison of frequency directed LV lead placement versus standard LV lead placement. Additionally, we will measure the time required to sense the signals paced at each LV site to the RV electrode and vice versa.

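### Does letting the observed variability set enrolment between 20 and 30 spoil the variance the study is meant to deliver?

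*Protocol*

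**What the plan says.** The Research procedures section gives the target as enrolment "for a total of 20-30 subjects (depending on the encountered variability of results"), with near-equal numbers of men and women. It does not say which measure of variability is meant, when it is examined, or whether more variability means more patients.

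The Background section explains the purpose. At present "the effect of various locations of LV pacing sites on the resultant QRS frequency characteristics is not precisely known within any given patient", and the data are gathered "in order to determine the variability in frequency signals between known locations". The later trial is to be designed by "utilizing the variance of frequency results we determine in this study to determine the study size required and specific frequency goals".

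Research procedures returns to this at its end. The analysis will "compare the frequency data from these QRS segments between the nine different ventricular locations to derive the positional variability", after which the investigators expect to "determine the sample sizes required for a randomized comparison of frequency directed LV lead placement versus standard LV lead placement". No hypothesis test is described for the present study.

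**The concern.** Set side by side, these statements make variability both the study's product and the thing that decides when data collection ends. If enrolment stops at 20 because the results look consistent, low variance estimates are kept as they stand, while high ones are diluted by up to ten more patients. The average reported variance is then too low. The opposite rule would make it too high.

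The estimate is the main number handed to the next trial, and an understated variance would make that trial too small. With no rule on the page, the end of enrolment could also be chosen after seeing the data, and no outside reader could work out the bias. Naming one number between 20 and 30 looks like a costless repair.

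**Working it through.** **The plan's own figure.** The range 20 to 30 cannot be reproduced. The protocol gives no standard deviation, precision target or effect size behind it. What can be checked is how far a data-dependent stop inside that range could move the variance estimate.

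**Inputs.** From the protocol: a minimum of 20 patients, a maximum of 30, and nine sites per patient. Assumed: normal data, true variance 1, one look at 20 patients, stopping if the variance is below c times its true value and otherwise going on to 30. Two targets are possible:

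- Variance among sites within a patient. Nine sites give 8 degrees of freedom per patient if all are reached and independent, so d20 = 8 × 20 = 160 and d30 = 8 × 30 = 240.
- Variance between patients: d20 = 19, d30 = 29.

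**Bias.** With F(x; d) the chi-square distribution function,

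bias = −(1 − d20/d30) × [F(c·d20; d20) − F(c·d20; d20 + 2)].

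At c = 1:

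- Within: (1 − 160/240) × (0.5149 − 0.4703) = 0.3333 × 0.0446 = 1.49% low.
- Between: (1 − 19/29) × (0.5432 − 0.4149) = 0.3448 × 0.1283 = 4.42% low.

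The single-look maximum is at c = 1 in both cases:

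| c | 0.67 | 0.8 | 0.9 | 1.0 | 1.1 | 1.25 | 1.5 |
|---|---|---|---|---|---|---|---|
| Within, % low | 0.01 | 0.23 | 0.97 | 1.49 | 1.02 | 0.17 | 0.00 |
| Between, % low | 2.26 | 3.55 | 4.20 | 4.42 | 4.23 | 3.43 | 1.80 |

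Reversing the rule gives the same amounts high. Simulated looks after every patient from 20 onward give maxima of about 1.5% and 4.5%.

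**Against sampling error.** The relative standard error of a variance is √(2/d). At 20 patients it is √(2/160) = 11.2% within and √(2/19) = 32.4% between. The worst bias is therefore 1.49/11.2 = 0.13 and 4.42/32.4 = 0.14 of a standard error. The 95% limits for the standard deviation at 20 patients are 0.90 to 1.12 times the estimate (within) and 0.76 to 1.46 times (between).

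**If sites are correlated.** Three sites share each vein, so 8 degrees of freedom per patient may be generous and 1.5% is not a strict ceiling. As an extreme, let each vein act as one site: 2 degrees of freedom per patient, d20 = 40, d30 = 60. At c = 1 the bracket in the formula equals 20^20·e^(−20)/20! = 0.0888, so the bias is 0.0888/3 = 3.0% low. The standard error rises too, to √(2/40) = 22.4%, and the ratio is again 0.13.

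**Would a fixed number be more accurate?** Root mean square error of the variance, with simulation for the stop-if-low rule and √(2/d) for fixed numbers:

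| Plan | Within | Between |
|---|---|---|
| Stop if low, c = 1 (mean n 24.9 within, 24.6 between) | 0.101 | 0.284 |
| Fixed 20 | 0.112 | 0.324 |
| Fixed 25 | 0.100 | 0.289 |
| Fixed 30 | 0.091 | 0.263 |

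For the between-patient variance at c = 1.25, the adaptive rule has error 0.279 at mean n 22.1, better than fixed 25 and better than fixed 22 (√(2/21) = 0.309). At c = 0.8 it has 0.291 at mean n 27.1, worse than fixed 27 (√(2/26) = 0.277). The reverse rule at c = 1 gives 0.103 within and 0.305 between at mean n of 25.2 and 25.4, somewhat worse than fixed 25. The ordering depends on a rule the protocol does not state.

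**The case for a change.** The best case for a change is that the protocol itself ties the number of patients to the result. A statistical analysis plan could spell out the rule, but a rule driven by the observed variance would still bias that variance. The bias falls on the quantity the study exists to deliver, an open rule allows a choice after the data are seen, and one sentence naming 25 patients would end the matter at about the same error as a one-look rule averaging 25.

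Part of this stands. The dependence is on the page, and under the assumed rules the bias is real. The rest is weaker:

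- The bias needs the stopping measure to be the estimated variance. The study records limb leads and V3, three parts of the QRS, left ventricular pacing alone and with right ventricular pacing, conduction times, and procedure and fluoroscopy times. Stopping on one of these, or on a general impression, carries over only in part to the variance of another.
- The measure, look time and threshold are details that a statistical analysis plan commonly holds. That plan is not available here, so their absence from the protocol is not a defect.
- The fixed number has a price. Above 20, it commits five (25) or ten (30) more patients than the minimum to the study pacing and fluoroscopy, and it removes the option to collect more data when results prove variable. In a small planning survey that option is a defensible preference.

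**Conclusion.** The concern identifies a true feature of the design, but it does not call for a change. If the stopping measure is the variance being estimated, the estimate could be off by at most about 1.5% (within patients, nine independent sites) or about 4.5% (between patients, allowing repeated looks), in a direction set by the unstated rule. Under a single look this is about 0.13 standard errors whichever target is meant, and whether or not sites in a vein move together. The next trial's designers will face far more uncertainty from having only 20 to 30 patients.

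Fixing the number removes a small possible bias without a demonstrated gain in accuracy, at the cost of flexibility and, above 20, of patients who might not have been needed. That is a fair trade-off. Because the range starts at 20, the variance in the first 20 patients does not depend on the stop (simulated mean 1.000 for both targets). An analyst can set it beside the final estimate from data already in hand, bearing in mind that it is the noisier of the two.

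These figures assume normal data, no stop before 20 and the stopping rules described.

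### Does the protocol contradict itself by giving added time for three sites when nine are mapped, and by timing each site over a single interval?

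*Protocol*

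**What the plan says.** All the relevant text is in the protocol, under Research procedures. The guidewire "will be advanced into 3 coronary sinus branch veins receiving venous blood from the anterior, lateral and posterior regions of the left ventricle". Within them, "In each branch vein, 3 pacing sites will be tested: apical, mid ventricular and basal". The order is fixed: "We will test the anterior and posterior veins first, and then test the usually targeted lateral vein". Once the lateral vein is finished, the standard LV lead is passed over the same guidewire.

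The burden sentence comes next. It concerns "The additional time required to position and pace the 3 sites (alone and in combination with a previously implanted RV pacing lead") and says that this time "should not exceed 5-10 minutes, with <2 minutes of fluoroscopy. In this manner, nine distributed sites around the LV will be assessed".

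The same paragraph ends with the timing measure. Its wording, for procedural and fluoroscopic time alike, is: "locate and test each site will be measured starting after placing the coronary sinus delivery sheath until the delivery of the LV lead". The following paragraph uses all nine sites, because the frequency data are compared "between the nine different ventricular locations to derive the positional variability".

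**The concern.** Two things look wrong on a first reading.

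- **The burden figure and the procedure do not obviously match.** The only statement of added time and fluoroscopy refers to three sites, while each patient has nine mapped. The sentence before it is about the lateral vein alone; the one after it is about all nine sites. If the figure is per vein, no nine-site total is given. If it was meant for all nine, the count of three is wrong. The two readings differ by a factor of three in procedure time and in fluoroscopy.

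- **The timing measure names one unit and bounds another.** It promises a time for each site, but its start (after sheath placement) and its stop (lead delivery) each occur once per patient. Taken literally, it gives one duration spanning three veins, including some work in the lateral vein that would be done anyway.

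At stake would be a reader's view of what the study adds to a routine implant, and whether site-level times are collected at all.

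**Working it through.** **Inputs, all from Research procedures:** 3 veins; 3 sites per vein; 5-10 minutes added; under 2 minutes of fluoroscopy; 20-30 subjects.

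**Reproducing the plan's own count.** Sites per patient = veins × sites per vein = 3 × 3 = 9, which agrees with "In this manner, nine distributed sites around the LV will be assessed". The 5-10 minute and 2 minute figures are planning estimates with no stated derivation. They can be scaled but not reproduced.

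**Burden under each reading.**

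| Reading of the figure | Procedure time per patient | Fluoroscopy per patient | Time per site | Fluoroscopy per site |
|---|---|---|---|---|
| Per vein, veins costing the same (assumption) | 3 × 5 = 15 to 3 × 10 = 30 min | under 3 × 2 = 6 min | 15/9 = 1.7 to 30/9 = 3.3 min | under 6 × 60/9 = 40 s |
| All nine sites | 5 to 10 min | under 2 min | 5/9 = 0.6 to 10/9 = 1.1 min | under 2 × 60/9 = 13 s |

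**Which reading the text favours.** Apart from the burden sentence, the section mentions three sites twice. The first mention defines the apical, mid and basal sites within each vein. The second refers to the three sites in the lateral vein and immediately precedes the burden sentence. Both mean three sites in one vein. The sentence after the burden figure then says that nine sites are reached in this manner, which fits three sites repeated over three veins. On this reading no two statements conflict. The all-nine reading requires the number three to be a mistake, and nothing in the text suggests that it is.

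**The timing measure under each reading.**

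- One interval per patient: 20 to 30 durations in the study.
- One time per site: 20 × 9 = 180 to 30 × 9 = 270 durations.

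The sentence names each site as the unit and then gives a start and an end. It can therefore be taken as the window during which sites are timed in succession. On that reading only the operational start and stop for a site are unwritten.

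**What the single interval would still show.** All mapping happens after the sheath is in place and before the lead is delivered. Hence mapping time ≤ sheath-to-lead time in every patient. Even the literal reading gives an observed upper bound on the added time. An interval within the estimate would support it; a longer one would not refute it, because routine lateral-vein work is included.

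**Does anything depend on these times?** The Background section gives the purpose: to learn how QRS frequency varies between known pacing locations, so that a later trial can be sized. The enrolment range is tied to the variability of results, and the stated comparison is of frequency between locations. Neither the burden estimate nor the measured time enters any of these.

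**The case for a change.** The strongest case for a change is practical. If the figure is per vein, the only burden number printed covers a third of the sites. It may also be the third with the least extra work, since the lateral vein is normally targeted and receives the lead. A reader who took 5-10 minutes as the whole addition would be misled, and multiplying by three is that reader's own inference, which ignores time spent moving between veins. On timing, a duration not recorded during the procedure cannot be recovered later from a single interval, and no analysis plan could supply it. The remedy would be cheap: two sentences reworded and up to 18 readings per procedure (9 sites × 2).

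Much of this stands as fact. No nine-site total is stated, the three sites in the burden sentence are not tied to a named vein, and no start or stop for a site is written. What does not follow is that the plan is in error. The per-vein reading resolves the apparent conflict using the section's own vocabulary. When a site starts and stops is recording detail that operators can settle sensibly once told to time each site. The protocol also does not say that the measured time is meant to verify the 5-10 minute estimate, so it should not be faulted for failing to isolate the added portion.

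**Conclusion.** No change to the plan follows. The wording is ambiguous, but it is not contradictory. The natural per-vein reading implies about 15-30 minutes and under 6 minutes of fluoroscopy per patient, assuming the three veins cost the same and ignoring time between them. The less natural reading implies 5-10 minutes and under 2 minutes. The timing sentence either sets the window for 180-270 site times or yields 20-30 whole-procedure intervals; the latter would still bound the mapping time from above.

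The effect on the study's stated purpose is nil. The frequency comparison across nine sites, the enrolment range and the planned use of the variance are the same under every reading. Labelling the figure as per vein or total, and noting when a site's clock starts and stops, would be a courtesy to the reader; it corrects no fault in the design. This conclusion rests on timing being descriptive, as the protocol presents it. It would need another look if the times were to support a claim of their own, such as the feasibility of mapping in the later trial, which this protocol does not make.

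### The undivided positional variability from the nine-site comparison does not fix the gain of the guided-placement trial it is meant to size

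*Protocol*

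**What the plan says.** The Background states the gap in patient-level terms: "the effect of various locations of LV pacing sites on the resultant QRS frequency characteristics is not precisely known within any given patient". It also states the purpose of filling it: "We hope to begin a prospective trial to select the optimal LV pacing site based on paced QRS frequency characteristics". The later trial is to be designed by "utilizing the variance of frequency results we determine in this study to determine the study size required and specific frequency goals".

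Under Research procedures, three branch veins are mapped (anterior, lateral, posterior). For each of them, "In each branch vein, 3 pacing sites will be tested: apical, mid ventricular and basal". Location is therefore crossed with patient: 3 × 3 = 9 sites in the same person, in 20-30 people. The lateral vein is named as the customary target.

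The only analysis of location is this: "We will then compare the frequency data from these QRS segments between the nine different ventricular locations to derive the positional variability". The next sentence says that, with this in hand, it should be possible to determine the "sample sizes required for a randomized comparison of frequency directed LV lead placement versus standard LV lead placement". The protocol does not define positional variability. It does not divide it into components, and it describes no repeat capture at a site.

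**The concern.** The planned intervention chooses a site for each patient from that patient's own paced frequency data. Its gain over standard placement depends on three things: how far sites differ in ways common to everyone, how far they differ in ways peculiar to the patient, and where the standard site lies among the common differences. An undivided figure for variability between locations carries none of these separately.

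If one position is best in nearly everyone, a fixed placement rule captures the benefit and mapping each patient adds little. If the best position varies from patient to patient, mapping is what produces the benefit. Both situations can give the same positional variability. A sample size built on that number could be far too small or far too large, and the number would not show which.

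**Working it through.** **The plan's own figures.** Nine sites follows from 3 veins × 3 levels. The 20-30 subjects cannot be reproduced, because no alpha, power, effect, SD or precision target is given. The check is therefore whether positional variability determines the later trial's gain.

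**Model.** For patient i at site j: Y = P_i + L_j + I_ij + E_ij. Here P is the patient's level, L the location effect shared by all, I the patient-specific location effect and E the capture and manual-isolation error. P cancels within a patient, so positional variance V = var(L) + var(I) + var(E).

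**Assumptions.** V = 1, normal values, higher taken as more favourable, and E = 0 at first. None of these comes from the protocol.

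**Gain over a fixed standard site s.** G_s = mean of max_j(L_j + I_ij) − L_s. The expected maximum of nine standard normal values is 1.485 and the expected minimum is −1.485.

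- All variation patient-specific (L = 0): G_s = 1.485 − 0, about 1.5 SD whichever site is standard.
- All variation shared (I = 0): G_s = L_max − L_s. This is 0 if the standard site is the best, about 1.5 if it is average, and 1.485 + 1.485 = 2.97, about 3 SD, if it is the worst.

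**Gain over the single site best on average**, by simulation with V held at 1:

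| Share of V common to all patients | 0% | 25% | 50% | 75% | 100% |
|---|---|---|---|---|---|
| Large samples | 1.48 | 0.72 | 0.40 | 0.18 | 0 |
| Best common site picked from the same 25 patients | 1.19 | 0.68 | 0.39 | 0.18 | 0 |

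The second row is lower on the left because the apparent best common site is itself chosen from the data. At 0% shared, the nine location means have SD 1/√25 = 0.2, so the gain is 1.485 × (1 − 0.2) = 1.19. Pooled within-patient variance was 1.00 in every column.

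**Can the planned data separate the parts?** Yes, for shared against residual. In a patient-plus-location decomposition, var(L) is estimated by (MS_location − MS_residual)/n. It has 8 df for location and 8(n − 1) for the residual: 152, 192 and 232 for n = 20, 25 and 30. With true shared variance of 0, 0.25, 0.50, 0.75 and 1, the mean estimates at n = 25 were 0.00, 0.25, 0.50, 0.75 and 1.00.

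**What the split cannot do.** The residual is var(I) + var(E). Take shared variance 0.5 and n = 25:

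| Remaining 0.5 | Apparent gain over best common site | True gain |
|---|---|---|
| all genuine (I) | 0.39 | 0.39 |
| half I, half E | 0.39 | 0.05 |
| all error (E) | 0.39 | −0.30 |

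With one value per site, the observed data have the same distribution in all three rows. No statistic computed from single captures can tell them apart. In particular, the proportion of patients whose best site differs from the common best is the same in each.

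**The case against.** The strongest reply is that the protocol fixes no estimator. It does not say that the data will be reduced to one number, and three QRS thirds and several leads make one number unlikely. It does not rule out a within-patient analysis, and its rationale and crossed design point towards one. A model specification is ordinary SAP content. All of this is true, and it rules out several stronger readings that a reader might infer:

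- *That the study cannot answer the question.* The limit belongs to the undivided figure. The crossed data allow the split.
- *That the analysis ignores pairing and so inflates standard errors.* No unpaired analysis is stated.
- *That sample size is wrong by a definite factor.* Squaring 1.48/0.40 gives about 14, but that sizes a trial against the best common site. The protocol's comparator is standard placement, and the endpoint of the later trial is not stated.
- *That the variance is meant to decide whether guidance is worth testing.* The stated uses are study size and frequency goals.

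The point about the comparator also has force in the other direction. Against standard placement, shared differences are a legitimate part of the gain. Averaged over arbitrary standard sites, the gain is about 1.5 SD at every split.

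This does not rescue the step in the plan. There is one actual standard placement, not an average over arbitrary ones, and the 0 to 3 SD range shows that its position matters. Silence on the model could be left to a SAP. The stated claim that positional variability, once obtained, allows the trial to be sized is the protocol's own, and it does not follow.

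**Conclusion.** The concern holds in a limited form. The protocol neither defines positional variability nor commits to separating shared from patient-specific variation, yet it makes that quantity the basis for sizing a trial of per-patient site choice. At the same positional variance, the gain over standard placement is about 1.5 SD if variation is wholly patient-specific, and from 0 to about 3 SD if it is wholly shared. Over the best common site it is about 1.5 down to 0 SD.

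These sizes assume normal values, unit site variance, no measurement error and a gain measured on the frequency scale. They show what the figure leaves open and do not predict the trial's result. Nothing is lost in the data collection as planned, so this is an improvement that should be made to the analysis and not a flaw in the design.

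**What to change.** Replace the sentence with a within-patient analysis for each QRS third: a linear mixed model with vein (3) by level (3) as fixed effects and a random patient effect. Report:

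- (a) the shared location variance, corrected for sampling error;
- (b) the residual within-patient variance, labelled an upper bound on patient-specific variation because it includes capture and manual-isolation error;
- (c) the mean and between-patient SD of two within-patient differences: most favourable site minus the customary lateral-vein site, and most favourable site minus the site best on average.

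State beforehand which frequency direction counts as favourable and which of the three lateral levels represents standard placement in this analysis. Label (c) as optimistic, because the best site is picked from noisy values. Where the saved recordings already hold several paced beats per site, use them to estimate within-site error. Beats from one wire position show beat-to-beat and isolation error but not repositioning error.

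Base the later trial's assumed gain and sample size on (c), not on total nine-site variability. The between-patient variance that a parallel-group calculation also needs comes from the same model. If the later endpoint is not paced frequency, a separate link to that endpoint is needed.

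The cost is slightly more analysis work, with no added patients, sites or procedures. The quoted gain may come out smaller.

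### The planned positional variability pools spread between veins with spread along a vein; splitting the two costs nothing and would inform the next trial better

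*Protocol*

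**What the plan says.** Under Research procedures, the Protocol has a guidewire advanced into "3 coronary sinus branch veins receiving venous blood from the anterior, lateral and posterior regions of the left ventricle". It continues: "In each branch vein, 3 pacing sites will be tested: apical, mid ventricular and basal". The same three levels recur in every vein, so a patient with complete data contributes a crossed layout of vein (3) by level (3), nine sites in all. The lateral vein is described as the one normally aimed for, and the permanent lead is delivered there after testing.

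The paragraph on frequency analysis states one comparison of the segment frequencies: "between the nine different ventricular locations to derive the positional variability". It names neither vein nor level as a source of variation. It says this result should then allow calculation of the "sample sizes required for a randomized comparison of frequency directed LV lead placement versus standard LV lead placement". The Background gives the same purpose: "utilizing the variance of frequency results we determine in this study to determine the study size required and specific frequency goals". Enrolment is planned "for a total of 20-30 subjects (depending on the encountered variability of results").

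**The concern.** Positional variability is what this study is meant to deliver to the next one. If it is delivered as a single figure over nine locations, it merges two quantities that mean different things for a trial of directed placement.

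- If nearly all the spread lies between veins, the three sites in the lateral vein are almost interchangeable. Directed placement can then differ from customary placement only by leaving that vein.
- If nearly all the spread lies along each vein, there is as much to choose from within the lateral vein as across the ventricle.

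The contrast between directed and standard placement that the next trial could expect is not the same in these two cases, even when the pooled variance is identical. The layout already collects what is needed to tell them apart.

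**Working it through.** **Plan's own figure.** The 20 to 30 subjects come with no SD, effect size, error rate or power, so there is nothing to reproduce.

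**Inputs from the Protocol (Research procedures).** 3 veins, 3 levels, 9 sites per patient, n = 20 to 30.

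**Assumptions (the documents give no values).** Complete data; all quantities in units of an assumed SD or variance of 1. V is the vein-within-patient variance and S the site-within-vein variance. ρ is the share of within-patient residual variance common to the three sites of a vein, taken from 0 to 1.

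**Step 1. What a pooled variance contains.** The sample variance over a patient's nine sites has 8 df: 2 between veins (expected mean square 3V + S) and 6 within veins (expected mean square S). Its expectation is

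[2(3V + S) + 6S] / 8 = 0.75V + S.

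Three quite different splits give the same pooled value:

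| V | S | Pooled 0.75V + S | Variance of a difference, two sites in the same vein (2S) | Variance of a difference, sites in different veins (2V + 2S) |
|---|---|---|---|---|
| 0 | 1.00 | 1.00 | 2.00 | 2.00 |
| 0.57 | 0.57 | 1.00 | 1.14 | 2.29 |
| 1.33 | 0 | 1.00 | 0 | 2.67 |

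(Rows 2 and 3 use the unrounded values 4/7 and 4/3.) With the pooled figure fixed at 1.00, the spread available inside one vein runs from 2.00 to nothing. The pooled figure alone cannot say which row applies.

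**Step 2. Is precision lost for individual sites?** No. Vein, level and vein-by-level together are saturated and have the same nine cell means. In complete data the vein means are exact averages of the nine site means; a numerical check gave identical values. Dropping the interaction would add only 4 error df (152 to 156 at n=20; critical t 1.9757 against 1.9753).

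**Step 3. Where the layout does help: a whole-vein question.**

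- SE of a difference between two site means = √(2/n): 0.316 at n=20 and 0.258 at n=30.
- SE of a difference between two vein means = √(2[ρ + (1−ρ)/3]/n): at ρ = 0, 0.183 and 0.149.
- Ratio of the first to the second: 1.73, 1.41, 1.22, 1.10 and 1.00 at ρ = 0, 0.25, 0.5, 0.75 and 1.

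These SEs belong to different questions (one site, or a vein as a whole). The ratio shows how fast the benefit of averaging disappears; it does not compare two analyses of the same question.

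**Step 4. Power for an assumed pure vein effect of −0.25, 0, +0.25 SD, ρ = 0, 5% level.** Noncentrality = n × 3 × (2 × 0.25²): 7.5 at n=20 and 11.25 at n=30. Error df = 8(n−1): 152 and 232. From the noncentral F:

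| n | Nine-site test (8 df) | Vein test (2 df) |
|---|---|---|
| 20 | 43% | 68% |
| 30 | 63% | 86% |

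If a vein-within-patient term is fitted, the vein test uses 2(n−1) = 38 or 58 error df. The same noncentralities then give 65% and 84%, which leaves the picture unchanged. ρ = 0 is the case most favourable to the vein test; its advantage shrinks as ρ rises.

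**The case against.** The sentence on comparing locations states an intention. It names no model, test or variance estimator, does not say the sites will be treated as unstructured, and does not exclude a vein-by-level analysis. Model terms usually belong in an SAP, which is not shown. Each location is itself defined by its vein and level, so a nine-location comparison is the same layout in full. All of this stands, and it is why the point is not an error in the plan.

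A reader might infer three stronger claims that the documents do not support:

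- **That comparing nine locations loses precision in general.** It does not, because the factorial model is saturated with the same nine means. Only whole-vein and whole-level questions gain, and only to the extent that sites within a vein are not strongly correlated.
- **That the study cannot separate the two sources of spread.** The data are collected by vein and level, so the split can be made. Only a single pooled summary would hide it.
- **That the next trial will be sized on a best-of-nine gain, or must choose between one and three sites per vein.** The Protocol plans no such calculation and poses no such question, although it does record time and fluoroscopy for each site.

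What the objection does not remove is that the Protocol itself names the quantity passed to the sample-size step, and that quantity, reported as one figure, is less informative than the design allows.

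**Conclusion.** The point holds as a free improvement. The Protocol builds a 3 × 3 within-patient layout but describes only a nine-location comparison leading to one positional variability. The non-identifiability of the split from a pooled variance (0/1.00, 0.57/0.57 and 1.33/0 all giving 1.00) is algebra and does not depend on the data. It matters because the Protocol uses this variability to plan directed against standard placement and identifies the lateral vein as the customary target.

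The power figures (43% against 68% at n=20, 63% against 86% at n=30) are illustrative. They assume a pure vein effect of ±0.25 SD around the middle vein, independent site errors and complete data. They concern a whole-vein effect only. How much the split would change the next trial's sample size cannot be stated, because the documents give no variance and no correlation.

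**What to change.** In the frequency-analysis paragraph of Research procedures, replace the undifferentiated nine-location comparison with an analysis of the sites within patient:

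- Fixed terms for vein, level and vein-by-level; random effects for patient and for vein within patient.
- Report the nine site means as now, together with the vein and level differences.
- Report between-vein and along-vein variance separately, each with a confidence interval. With 20 to 30 patients these intervals should be shown, not just the point estimates.
- State that both components, not one pooled figure, go into the sample-size calculation for the trial of directed against standard placement.

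A comparison of one with three mapped sites per vein, set beside the recorded time and fluoroscopy, could be added but is optional.

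Cost: analysis wording only. No added patients, data or procedures.
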